#### **6.3.1.2. Pembrolizumab administration**

Pembrolizumab will be administered using IV infusion on Day 1 of each 3-week treatment cycle after all procedures and assessments have been completed.

Pembrolizumab will be administered as a dose of 200 mg using a 30 min IV infusion after at least approximately 1 hour rest period after completion of belantamab mafodotin infusion. Premedication is not required prior to infusion unless deemed medically necessary, in which case it should be administered according to institutional recommendations.

In case of IRR during or after preceding belantamab mafodotin infusion, the administration of pembrolizumab will be delayed to allow for recovery to Grade 1 or less. In total, the infusion of pembrolizumab may be delayed for up to the allowed +3 day window from the scheduled dose date to allow for recovery, and to accommodate scheduling conflicts in a given cycle. If the subject does not recover from IRR to Grade 1 or less within the +3 day window, the dosing of pembrolizumab will be skipped in a given cycle, and may be resumed in the next cycle.

All subjects are required to remain under observation at the study site for at least three hours post-infusion of the last study drug administered for the first two study treatment dosing visits. At subsequent study treatment dosing visits, for subjects who experience infusion-related reactions, the post-infusion observation time should remain as at least three hours; for subjects who do not experience infusion reactions, these subjects should remain under observation for a time period not shorter than one hour (or longer as per the judgement of the investigator or as per institutional guidelines.)

In case of IRR during pembrolizumab administration –please refer to [Table 6](#) for management guidelines.

Detailed information on the preparation and administration, refer to [[Keytruda SmPC, 2017](#) and [KEYTRUDA PI, 2018](#)].

### **6.4. Planned Dose Adjustments**

#### **6.4.1. Adjustments due to body weight**

The actual body weight in kg at the baseline (assessed on the Cycle 1 Day prior to dosing) will be used for dose calculation of belantamab mafodotin in all subjects during

the treatment period. However, if the change of body weight is greater than 10%, the dose should be re-calculated based on the actual body weight on the day of dosing.

A fixed dose of pembrolizumab will be used during the study.

#### **6.4.2. Intra subject dose escalation**

For subjects enrolled in Part 1 intra-subject dose escalations of belantamab mafodotin may be considered on a case-by-case basis, provided that the subject completed at least 2 cycles at originally assigned dose, has tolerated treatment well, and did not experience the treatment related Grade 3 or higher toxicity. A subject's dose may be increased to that of a completed cohort that has not exceeded the maximum pre-specified dose of 3.4 mg/kg. Approval must be obtained from a GSK Medical Monitor. Dose-escalation decisions will be documented on a Dose Escalation/De-escalation Decision Form (see SRM).

### **6.5. Subject Specific Dose Adjustment Criteria**

#### **6.5.1. Dose modifications and management for belantamab mafodotin-related toxicity**

Subjects should have their dose (including the first dose and subsequent doses) delayed or reduced for toxicities according to the recommendations as listed in [Table 4](#). Dose reductions are only allowed for belantamab mafodotin.

In individual cases where, in the judgement of an investigator, waiting a full planned Cycle (21 days) to resume treatment after delays due to toxicities would be detrimental to the subjects' health, the Medical Monitor should be contacted to discuss an earlier re-start. An earlier re-start may be considered only for subjects who have recovered from toxicity to Grade 1 or less. Dosing cannot occur more frequently than every 21 days ( $\pm 3$  days). In such cases, efficacy and safety assessments must remain every 3 weeks from the initial efficacy and safety assessments (Cycle 1 Day 1), which may result in 2 separate visits (1 for disease assessment [[Table 8](#)] and 1 for dosing [[Table 9](#)]).

No dose reductions are allowed for pembrolizumab. Dose Modification Guidelines for Pembrolizumab-Related Adverse Events are listed in [Table 5](#).

If belantamab mafodotin is held or discontinued for any toxicity, pembrolizumab is to be held or discontinued.

For drug related toxicities which are not listed in [Table 4](#) and [Table 5](#), the general rule of withholding the dose at Grade 3 or greater toxicity should be followed.

Resuming treatment will be possible with or without dose reduction after the toxicity has resolved to Grade 1 or less, and in agreement between PI and GSK Medical Monitor.

**Table 4 Dose Modification Guidelines for Belantamab Mafodotin-Related Adverse Events**

Toxicity	Grade	Recommendations to belantamab mafodotin	Recommendations to pembrolizumab
Serum creatinine elevation or decrease in eGFR which cannot be explained by concomitant sepsis, TLS, other severe infection with fever or dehydration	If absolute serum creatinine increase from baseline of >0.5 mg/dL	
 
Repeat serum creatinine within 48 hours
 
If confirmed: withhold therapy, institute treatment and monitoring as clinically indicated, and follow for resolution
 
Discuss any further dosing with Medical Monitora
 
	See Table 5 for guidance on pembrolizumab
Serum creatinine b >Grade 3 (acute kidney injury)	>3.0mg/dL from baseline Or 3.0-6.0xULN	
 
Provide appropriate medical treatment.
 
Permanently discontinue treatment with belantamab mafodotin
 
	Resume treatment with pembrolizumab only if treatment with belantamab mafodotin may be continued
Spot urine (albumin / creatinine ratios)	>2000 mg/g (or 224 mg/mmol)	
 
Re-test (at least 7 days apart).
 
If not confirmed, continue belantamab mafodotin at current dose
 
If confirmed on re-test and no clear evidence of disease progressionc 
 
Interrupt treatment with belantamab mafodotin
 
Repeat testing within 4 weeks 
 
If spot urine <2000 mg/g (224/mg/mmol) may restart belantamab mafodotin with one dose level reduction
 
If spot urine remains >2000 mg/g (224/mg/mmol) after 4 weeks; permanently discontinue belantamab mafodotin and discontinue study treatment; provide treatment as clinically indicated and follow for resolution
 
 
 
 
 
	Resume treatment with pembrolizumab only if treatment with belantamab mafodotin may be continued
Thrombocytopenia (on days of dosing) )	3-4	
 
Withhold treatment until thrombocytopenia recovered to Grade 2 or less (≤G2).
 
If Grade 3-4 thrombocytopenia is considered disease-related, treatment may be continued with dose reduction and more
 
	Delay treatment until the next belantamab mafodotin dose

Toxicity	Grade	Recommendations to belantamab mafodotin	Recommendations to pembrolizumab
		
 
• frequent hematology monitoring, until recovery to Grade 2 or less.
 
• Implement supportive treatment (e.g. transfusion) as clinically indicated and per local practice.
 
	
Febrile neutropenia	Defined as: single temp of 38.3°C, or sustained 38°C for >1 hr AND ANC <1.0x10  /L	
 
• Withhold belantamab mafodotin and pembrolizumab and hospitalize subject with appropriate management, per local institutional guidance
 
• Consider additional supportive treatment per local guidance (e.g., growth factors)
 
• Upon recovery, consider a dose reduction of belantamab mafodotin, if neutropenia was drug related
 
	
 
• Delay treatment until the next belantamab mafodotin dose
 

Neutropenia	≥3 (Defined as ANC <1.0x10  /L)	
 
• If noted on Day 1 of any cycle, withhold belantamab mafodotin. Repeat hematology (CBC) as clinically indicated until recovery to Grade 2 or less.
 
• Resume belantamab mafodotin at pre-hold dose once neutropenia recovers to Grade ≤2 CCI [REDACTED] on Day 1 of the subsequent cycle.
 
• Implement supportive care as clinically indicated per local practice
 
	
 
• Delay treatment until the next belantamab mafodotin dose
 

	In case of recurrence of frequent episodes of neutropenia CCI [REDACTED]	
 
• Consider dose reduction of belantamab mafodotin, if it was drug-related.
 
	
 
• Delay treatment until the next belantamab mafodotin dose
 

Belantamab mafodotin Treatment Related Corneal events b	Corneal Management Care Regardless of Grade	Preservative-free artificial tears: 
 
• Increase to 1 drop as frequently as every 2 hours, as needed
 
	
	Grade 1 per GSK Scale	
 
• Continue treatment with current treatment with belantamab mafodotin
 
	
 
• None
 

Toxicity	Grade	Recommendations to belantamab mafodotin	Recommendations to pembrolizumab
	Grade 2 per GSK Scale	
 
• If Grade 2 finding (visual acuity and/or exam finding) and the subject is asymptomatic, continue dosing with belantamab mafodotin.
 
• If Grade 2 finding (visual acuity and/or exam findings) and the patient is symptomatic. 
 
○ DOSE REDUCE and continue treatment.
 
○ If already on 1.92 mg/kg, subject may continue at current dose.
 
 
 
• Upon improvement of either visual acuity or ophthalmic exam findings to <math>\leq</math>Grade 1 and improvement in symptoms, dose may be re-escalated to previous dose.
 
	
 
• Hold/Delay treatment until the next belantamab mafodotin dose
 

	Grade 3 per GSK Scale	
 
• If Grade 3 finding (exam finding) and the subject is asymptomatic: continue dosing with belantamab mafodotin.
 
• If Grade 3 exam finding and the subject is symptomatic or Grade 3 visual acuity: 
 
○ HOLD belantamab mafodotin . Upon improvement of either visual acuity or ophthalmic exam findings to <math>\leq</math> Grade 2 and improvement in symptoms continue treatment with dose REDUCTION.
 
○ If already on 1.92 mg/kg subject may continue at current dose
 
 
 
• If after event resolution eye symptoms are considered stable for at least 3 cycles consider re-escalation to previous dose.
 
	
 
• Hold/Delay treatment until the next belantamab mafodotin dose
 

	Grade 4 per GSK Scale	
 
• Hold treatment with belantamab mafodotin.
 
• Treatment re-start may be possible after discussion and agreement between the treating ophthalmologist*, treating physician, the GSK Medical Monitor
 
• *or optometrist, if an ophthalmologist is not available
 
	
 
• Stop treatment with pembrolizumab.
 
• Further treatment only possible if belantamab mafodotin is allowed to restart
 

Toxicity	Grade	Recommendations to belantamab mafodotin	Recommendations to pembrolizumab
Infusion Reaction c	2	Stop the infusion, provide medical treatment and continue at slower pace after resolution to Grade 0-1	See Table 6 for guidance on pembrolizumab
	3	Further treatment with belantamab mafodotin needs to be discussed with Medical Monitor. Continuation only allowed after recovery to $\leq$ Grade 1 and with pre-medication, and extension of infusion time to 2-4 hours. Any future infusion needs to be pre-medicated	
	4	Permanently discontinue	
Pneumonitis	2	Continue when toxicity resolves to Grade 0-1	See Table 5 for guidance on pembrolizumab
	Grade 3-4	Permanently discontinue	Permanently discontinue

- a. Medical Monitor may consult GSK's nephrotoxicity panel about plans to continue therapy
- b. Corneal toxicity should be graded according to GSK scale for belantamab mafodotin treatment related Corneal Events ([Appendix 9](#)).
- c. If symptoms resolve within one hour of stopping drug infusion, the infusion may be restarted at 50% of the original infusion rate (e.g., from 100 mL/hr to 50 mL/hr). Otherwise dosing will be held until symptoms resolve and the subject should be premedicated for the next scheduled dose

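### Table 4, Grade 3 corneal row: the restart condition can be met while a hold criterion of the same row still applies

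*Protocol*

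**What the plan says.** All wording is from the protocol, Section 6.5.1, Table 4, rows for belantamab mafodotin treatment related corneal events, unless stated otherwise.

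- Grade 3, dosing continues: "If Grade 3 finding (exam finding) and the subject is" asymptomatic. This bullet names the exam finding only. The matching Grade 2 bullet names visual acuity as well.
- Grade 3, hold trigger: "If Grade 3 exam finding and the subject is" followed by "symptomatic or Grade 3 visual acuity".
- Grade 3, restart: "HOLD belantamab mafodotin . Upon improvement of either visual acuity or ophthalmic exam findings to" at most "Grade 2 and improvement in symptoms continue treatment with dose" reduction.
- Lowest dose: the Grade 2 row says "If already on 1.92 mg/kg, subject may continue at current dose". The Grade 3 row carries the same line, so restart at that level involves no reduction.
- Grade 2, after a dose reduction for symptomatic findings: once either measure is at most "Grade 1 and improvement in symptoms, dose may be re-escalated to previous dose".
- Section 6.5.1 also holds pembrolizumab whenever belantamab mafodotin is held.

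**The concern.** A hold rule and a restart rule for the same toxicity should not give opposite instructions for the same patient on the same day. Here the trigger uses acuity, exam and symptoms, while restart needs only one of acuity and exam to recover, plus some easing of symptoms.

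Take a subject held with both measures at Grade 3. The exam falls to Grade 2, symptoms ease, and acuity stays at Grade 3. The restart sentence says continue. On the natural reading, the trigger sentence still says hold.

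At stake is redosing while a criterion that forced the hold persists, and sites resolving the clash differently. The row is likely to be used: Section 2.2.5 reports corneal events in 24 of 35 subjects and Grade 3 events in 5 of 35 in Part 2 of the monotherapy study at 3.4 mg/kg. The regimen differs, and the grading scale may differ, so these figures are no rate for this trial.

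**Working it through.** The plan gives no figure to reproduce. The check is of rule logic.

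**Two readings of the trigger**

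- Natural: hold if acuity is Grade 3, or if the exam is Grade 3 with symptoms. In support, the continue-dosing bullet covers only an exam finding without symptoms, so Grade 3 acuity is never allowed to continue there.
- Grouped: hold if the exam is Grade 3 and the subject has symptoms or Grade 3 acuity. In support, the underlining in the row runs across the symptom and acuity words as one unit.

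**Restart as written:** a measure that was Grade 3 is now Grade 2 or less, and symptoms are lower than at the start, either gone or milder.

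**Enumeration.** Start with acuity 3, exam 3 and symptoms. With improved symptoms there are 2 (acuity) × 2 (exam) × 2 (none, milder) = 8 re-check states. In two of them both measures are still Grade 3, so 8 − 2 = 6 meet restart:

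| Acuity | Exam | Symptoms | Hold still met, natural | Hold still met, grouped | Restart after the fix |
|---|---|---|---|---|---|
| ≤2 | ≤2 | none | no | no | yes |
| ≤2 | ≤2 | milder | no | no | yes |
| ≤2 | 3 | none | no | no | yes |
| ≤2 | 3 | milder | **yes** | **yes** | no |
| 3 | ≤2 | none | **yes** | no | no |
| 3 | ≤2 | milder | **yes** | no | no |

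Conflicts: 3 of 6 on the natural reading, 1 of 6 on the grouped reading. After the fix, 3 states allow restart and none conflicts on either reading.

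**Dependence on coding.** With separate grades 0 to 3, and improvement within Grade 2 or less also counted, the natural reading gives 6 (acuity stays 3) + 3 (exam stays 3 with symptoms) = 9 conflicts from a start with both at Grade 3. Starts with only one measure at Grade 3 and the other at Grade 2 add 2 + 4 = 6, for a total of 15. The conflict exists under either coding; its count does not measure frequency.

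**Does another provision settle it?**

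- Section 5.4.1.7 requires detailed case discussion for Grade 4 only, and sends restart back to Table 4.
- The last sentence before Table 4 in Section 6.5.1 allows resumption at Grade 1 or less with agreement of the investigator and medical monitor. It follows the rule for toxicities not listed in Tables 4 and 5. If it did govern here, it would contradict this row's Grade 2 threshold.
- Section 7.3.5 requires vision changes to be managed with the medical monitor and coordinating ophthalmologist, but does not say which instruction prevails.

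**The case against.** **The parse is open.** The underlining favours the grouped reading, on which the persistent-acuity example disappears. That stands: neither reading is proven. One conflict survives on both: acuity recovered, exam still Grade 3, symptoms milder but present.

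**The wording may be deliberate.** The same *either* appears in both rows, and the corneal rows accept dosing with persistent findings: an asymptomatic Grade 3 exam finding continues, and a symptomatic Grade 2 finding continues at a reduced dose. Partial recovery plus a lower dose could be the chosen rule. If so, the row should say that restart overrides a remaining hold criterion. It does not, and at 1.92 mg/kg there is no reduction to rely on.

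**Safeguards exist.** Table 4 gives guidelines, eye specialists and the medical monitor are involved (Sections 6.12.3 and 7.3.5), and Table 8 requires ocular exams before each of the first four doses. This limits harm, but it does not remove the contradiction.

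**Other rows prove little.** A reader might infer a drafting slip because other rows clear their trigger first, for example "Withhold treatment until thrombocytopenia recovered to Grade 2 or less". Those toxicities are graded on a single scale, so clearing the grade clears the trigger by construction, and the thrombocytopenia row has its own exception for disease-related cases. The comparison does not show intent.

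**Stronger readings are not supported.** A reader might infer that half of restarts would be unsafe, or that every one-sided recovery conflicts. The protocol gives no rate of discordant recovery, and a Grade 3 exam finding whose symptoms have fully resolved is not a conflict.

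**Conclusion.** The point holds as an internal contradiction in a patient-safety rule. In the Grade 3 corneal row, restart can coincide with persistent Grade 3 acuity or a persistent symptomatic Grade 3 exam finding on the natural reading, and with only the latter on the grouped reading. It should be fixed; confidence is medium.

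The conclusion rests on taking symptom improvement to include symptoms that are milder but still present. The grading tables in Appendix 9 are redacted, so how acuity and exam grades combine into an overall grade cannot be checked; the row itself names the two separately.

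A reader might infer that the Grade 2 row needs the same repair. From a start with both measures at Grade 2 and symptoms, 2 of 6 re-escalation states do still meet that row's dose-reduction criterion. But re-escalation there is only permitted, so the row does not give two opposing directions. No subject count, endpoint effect or sample-size effect is claimed.

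**What to change.** Keep the Grade 3 restart sentence, change its symptom condition to *improvement in any symptoms*, and insert before the instruction to continue:

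*and provided no hold criterion is still met (visual acuity is not Grade 3, and there is no Grade 3 exam finding with symptoms)*

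Keep the dose reduction and the 1.92 mg/kg line. Every existing restart requirement stays. The word *any* only lets a subject held for acuity loss without symptoms, who cannot literally show improved symptoms, restart once acuity recovers.

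Leave the Grade 2 row unchanged. Rewriting it to mirror the trigger would drop its present requirement that acuity or exam reach Grade 1 or less.

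Cost: one sentence at the next amendment, with no new data or patients. Holds of both drugs will be longer for subjects whose acuity and exam recover at different rates. The parenthesis also makes Grade 3 acuity alone a bar to restart, so a team that intended the grouped reading would be tightening the rule in the last two states of the table above and should decide that knowingly.

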## 5.4. Withdrawal/Stopping Criteria

Subjects will receive study treatment until disease progression, death or unacceptable toxicity (including but not restricted to meeting stopping criteria for significant toxicity as outlined in Section [5.4.1](#)), or completion of pre-assigned treatment by reaching a maximum of 35 treatment cycles. In addition, study treatment may be permanently discontinued for any of the following reasons:

- recurrent Grade 2 pneumonitis
- subject has met any of the protocol defined safety stopping criteria (Section [5.4.1](#))
- deviation(s) from the protocol
- request of the subject or proxy (withdrawal of consent by subject or proxy)
- investigator's discretion
- concurrent illness that prevents further administration of study treatment(s)
- study treatment must be permanently discontinued in case of pregnancy
- subject is lost to follow-up
- study is closed or terminated

The primary reason study treatment was permanently discontinued must be documented in the subject's medical records and electronic case report form (eCRF)

If the subject withdraws the consent and discontinues from treatment due to toxicity, 'adverse event (AE)' will be recorded as the primary reason for permanently discontinuation on the eCRF.

Once a subject has permanently discontinued from study treatment, the subject will not be allowed to be re-entered the study.

After the study treatment discontinuation, subjects will undergo end of treatment assessments 30 days ( $\pm 7$  days) after the last dosing, or prior to the start of new anti-cancer treatment (whichever occurs first). Subjects who discontinued treatment for reasons other than PD will be followed up every 3 weeks until confirmed PD, until initiation of a new anti-cancer therapy or death. All subjects with confirmed PD will be followed for OS and next subsequent anti-cancer therapy every 3 months until the end of study. End of study is defined in Section [5.5.2](#).

The following actions must be taken for subjects who fail to attend the clinic for a required study visit:

- The site must attempt to contact the subject and re-schedule the missed visit as soon as possible.
- The site must counsel the subject on the importance of maintaining the assigned visit schedule and ascertain whether or not the subject wishes to and/or should continue in the study.

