***Attribution of Toxicity:***

When study interventions are administered in combination, attribution of an adverse event to a single component is likely to be difficult. Therefore, while the investigator may attribute a toxicity event to the combination, to belantamab mafodotin alone, or to pembrolizumab alone, for adverse events listed in [Table 5](#), both interventions must be held according to the criteria in [[Table 5](#)].

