***Holding Study Interventions:***

When study interventions are administered in combination, if the AE is considered immune-related, both interventions should be held according to recommended dose modifications.

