***Restarting Study Interventions:***

Subjects may not have any dose modifications (no change in dose or schedule) of pembrolizumab in this study, as described in [Table 5](#). If the toxicity does not resolve or the criteria for resuming treatment are not met, the subject must be discontinued from all study interventions. If the toxicities do resolve and conditions are aligned with what is defined in [Table 5](#), the combination of belantamab mafodotin and pembrolizumab may be restarted at the discretion of the investigator.

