**Table 5 Dose Modification Guidelines for Pembrolizumab-Related Adverse Events**

General instructions:				

 
1. Severe and life-threatening irAEs, should be treated with IV corticosteroids followed by oral steroids. Other immunosuppressive treatment should begin if the irAEs are not controlled by corticosteroids.
 
2. Pembrolizumab must be permanently discontinued if AE does not resolve or the corticosteroid dose is <math>\leq 10</math> mg/day within 12 weeks of the last pembrolizumab treatment.
 
3. The corticosteroid taper should begin when the irAE is <math>\leq</math>Grade 1 and continue at least 4 weeks.
 
4. If pembrolizumab has been withheld, pembrolizumab may resume after the irAE decreased to <math>\leq</math>Grade 1 after corticosteroid taper.
 
				

Immune-related AEs	Toxicity grade or conditions (CTCAEv4.03)	Action taken to pembrolizumab	irAE management with corticosteroid and/or other therapies	Monitor and follow-up
Pneumonitis	Grade 2	Withhold	
 
• Administer corticosteroids (initial dose of 1 to 2 mg/kg prednisone or equivalent) followed by taper
 
• Add prophylactic antibiotics for opportunistic infections
 
	
 
• Monitor subjects for signs and symptoms of pneumonitis
 
• Evaluate subjects with suspected pneumonitis with radiographic imaging and initiate corticosteroid treatment
 
• 
 

	Recurrent Grade 2, Grade 3 or 4	Permanently discontinue		
Diarrhea / colitis	Grade 2 or 3	Withhold	
 
• Administer corticosteroids (initial dose of 1 to 2 mg/kg prednisone or equivalent) followed by taper
 
	
 
• Monitor subjects for signs and symptoms of enterocolitis (i.e. diarrhea, abdominal pain, blood or mucus in stool with or without fever) and of bowel perforation (i.e. peritoneal signs and ileus).
 
• Subjects with <math>\geq</math> Grade 2 diarrhea suspecting colitis should consider GI consultation and performing endoscopy to rule out colitis.
 
• Subjects with diarrhea/colitis should be advised to drink liberal quantities of clear fluids. If
 

	Recurrent Grade 3 or Grade 4	Permanently discontinue		

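### Table 4 lets belantamab mafodotin resume after Grade 2 pneumonitis without the recurrence stop or steroid-taper condition that Table 5, read with Section 6.5.2, applies to both drugs

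*Protocol*

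**What the plan says.** **Table 4 (Section 6.5.1), pneumonitis.** At Grade 2 the belantamab instruction is "Continue when toxicity resolves to Grade 0-1", and the pembrolizumab column refers to Table 5. At Grade 3-4 both drugs are permanently discontinued. Nothing separates a first from a later Grade 2 episode.

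**Table 5, pneumonitis.** A first Grade 2 event means withhold. The next row, "Recurrent Grade 2, Grade 3 or 4", means permanent discontinuation. The general instructions start the steroid taper once the event is at or below "Grade 1 and continue at least 4 weeks"; resumption follows the taper. The action column is headed for pembrolizumab.

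**Section 6.5.2.** Even when an event is attributed to belantamab alone, for events listed in Table 5 "both interventions must be held according to the criteria in" that table. The next paragraph is softer: "if the AE is considered immune-related, both interventions should be held according to recommended dose modifications". On restart, if the toxicity persists or the resumption criteria are not met, "the subject must be discontinued from all study interventions".

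**Section 5.4.** Recurrent Grade 2 pneumonitis heads a list introduced by "In addition, study treatment may be permanently discontinued for any of the following reasons". Section 6 defines study treatment as both drugs.

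**Section 6.12.4.** The treatment guidelines are meant for events the investigator judges related to pembrolizumab. An investigator who judges the event unrelated need not follow them.

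**The concern.** The same patient can receive different belantamab instructions depending on which table the site opens. Table 4 carries the Grade 3-4 stop from Table 5 but not the recurrent Grade 2 stop in the same Table 5 row, and it has no counterpart to the taper condition.

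Table 2 (Section 4.6.1) lists pneumonitis among toxicities the two drugs may share. It reports fatal cases with belantamab, with causality not established. Its mitigation column asks for evaluation, a delay of belantamab and a benefit/risk assessment, but sets no limit on recurrence. It sends the reader to Section 6.5.1 for belantamab and to Table 5 for pembrolizumab only, which is the route that leads to the incomplete row. What is at stake is re-dosing a subject whom Section 6.5.2 would keep off both drugs.

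**Working it through.** There is no planned figure to reproduce. The check is a comparison of texts, with one small count.

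**Recurrent Grade 2, resolved to Grade 0-1**

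1. Table 4 read alone: the only Grade 2 row applies, so belantamab may continue.
2. Table 5: recurrent Grade 2 is a permanent stop for pembrolizumab.
3. Section 6.5.2, attribution paragraph: pneumonitis is listed in Table 5, so both drugs follow Table 5 for the hold, even if the event is attributed to belantamab alone.
4. Section 6.5.2, restart paragraph: Table 5 gives no route to resumption after recurrent Grade 2, so the criteria for resuming cannot be met and all study interventions stop.
5. Result: one drug may continue under step 1, none under steps 2 to 4. Step 4 is an inference, because the attribution paragraph speaks of holding and Table 5's action column is for pembrolizumab.

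**What lets a site stay with Table 4**

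- Section 6.5.1 links the drugs in one direction only: "If belantamab mafodotin is held or discontinued for any toxicity, pembrolizumab is to be held or discontinued". The reverse is not stated there.
- The holding paragraph in Section 6.5.2 says should, and limits itself to events considered immune-related.
- Section 5.4 uses a permissive lead-in, although the pregnancy bullet in the same list says must.
- Section 6.12.4 makes the guidance depend on relatedness to pembrolizumab. This conflicts with the attribution paragraph of Section 6.5.2.

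**First Grade 2 episode, taper unfinished**

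Table 4 allows belantamab at Grade 0-1. Table 5 with Section 6.5.2 keeps both drugs on hold until after the taper.

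- Inputs: minimum taper 4 × 7 = 28 days (Table 5); cycle length 21 days (Section 4.2.1).
- Assumptions: the taper starts on the day the event reaches Grade 1 or less, it must be completed before restart, and dosing falls on scheduled days. The ±3-day window is ignored.
- Let d be the days since the last scheduled dosing day when the event reaches Grade 1 or less (d = 0 to 20). Count the scheduled days 0, 21, 42 that fall from day d up to, but not including, day d + 28.
- For d = 1 to 14, only day 21 falls in the window: 1 dose.
- For d = 0, days 0 and 21 fall in it: 2 doses. For d = 15 to 20, days 21 and 42 do: 2 doses.

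The answer is therefore 1 or 2 doses at the minimum taper. The documents do not say when in a cycle such events resolve, so no average is given.

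**The case against.** The strongest reply is that the protocol already deals with this. The attribution paragraph anticipates an event blamed on belantamab alone and still sends both drugs to Table 5. Section 5.4 names recurrent Grade 2 pneumonitis as a reason to stop study treatment. Table 4 is labelled as guidelines, whereas the attribution and restart paragraphs say must. On this view Table 4 is merely silent on recurrence, and a cross-reference is missing.

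Much of that stands. A reader might infer that Table 4 expressly orders re-dosing after recurrence, or that the protocol ignores recurrence; neither is supported. A reader might equally infer that one clear sentence stops both drugs for recurrent Grade 2, and there is none. The permissive verb in Section 5.4 is also weak evidence of discretion by itself, since the same list includes loss to follow-up and study closure.

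The dose count has limits too. Table 5's second general instruction brings in a 10 mg/day steroid threshold whose inequality, as printed, is hard to make sense of, so the need for a completed taper is not beyond doubt. Section 6.5.1 also permits an earlier restart after discussion with the Medical Monitor.

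The reply does not remove the problem. Table 4's only Grade 2 row is an affirmative instruction to continue on resolution, and Section 6.12.4 gives a site textual support for using that row alone.

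**Conclusion.** The inconsistency is real and should be corrected. Table 4's Grade 2 pneumonitis row lacks two conditions that Table 5, read with Section 6.5.2, places on both drugs. That recurrent Grade 2 stops both drugs is the better-supported reading. It rests on combining Table 5 with the attribution and restart paragraphs, with Section 5.4 in support and Section 6.12.4 against.

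For a recurrence, the difference is one drug continuing or none. For a first episode it is 1 or 2 belantamab doses, provided the taper of at least 4 weeks must be completed and dosing stays on the 21-day schedule.

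The documents give no pneumonitis rate for the combination, so the number of subjects affected cannot be stated. A reader might infer an effect on the response endpoint, the error rates or the sample size; nothing in the documents supports that. This is a point of subject safety and consistent conduct.

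**What to change.** Make three wording changes, limited to pneumonitis except where Section 6.12.4 is general:

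1. **Table 4.** Replace the pneumonitis rows with: *Grade 2, first episode: hold both drugs; restart per Table 5 and Section 6.5.2*, and *Recurrent Grade 2, or Grade 3-4: permanently discontinue both drugs*.
2. **Section 5.4.** State that study treatment must be permanently discontinued for recurrent Grade 2 pneumonitis, in the mandatory form the pregnancy bullet already uses.
3. **Section 6.12.4.** Add that the hold, restart and discontinuation rules in Section 6.5.2 and Table 5 apply to both drugs whatever the attribution. Without this, the conflict with the attribution paragraph remains.

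The cost is protocol text. Where sites already follow Section 6.5.2, subject management does not change. Where a site follows Table 4 alone, a few subjects would lose belantamab after a second Grade 2 episode, or restart it later after a first.
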